### 11.3.4 Definition of Outcome

The outcome of the AE should be recorded as one of the following:

**Resolved without sequelae** – The subject fully recovered from the adverse event with no observable residual effects.

**Resolved with sequelae** – The subject recovered from the adverse event with observable residual effects.

**Not resolved** – The adverse event was present at the time of last observation.

**Death** – The subject died as a result of the adverse event.

## 11.4 Immediately Reportable Events

### 11.4.1 Serious Adverse Events

Serious adverse events (SAE’s) must be documented and reported to the UFHCC DISC Safety Team **within 5 days** of learning of the event. The SAE Report and any email correspondence must be kept within the study files at the study site. The site investigator is responsible for informing the IRB and/or the Regulatory Authority of the SAE as per local requirements.

Follow-up information will be submitted to the UFHCC CRO stating that this is a follow-up to the previously reported SAE and giving the date of the original report. Each re-occurrence, complication, or progression of the original event should be reported as a follow-up to that event regardless of when it occurs. The follow-up information should describe whether the event has resolved or continues, if and how it was treated, whether the blind was broken or not (if applicable), and whether the participant continued or withdrew from study participation

The UFHCC Project Management Office (PMO) must also be notified of the SAE **within 24 hours** of knowledge of the event by email at [[contact]](mailto:[contact]).

#### 11.4.2 Other Events Requiring Immediate Reporting

All pregnancies, regardless of outcome, must be reported to the UFHCC DISC, including pregnancies that occur in the female partner of a male study subject. All pregnancies must be followed to outcome.

Although overdose (dose variance of >25%) and cancer are not always serious by regulatory definition, these events should also be reported to the DISC in an expedited manner. In case the overdose did not result in any adverse event, the Investigator should report this as “overdose, no adverse event” on the SAE form and provide the intended amount, as well as the actual amount, of drug administered. In the event of overdose or exaggerated response, appropriate supportive measures should be employed. Actual treatment should depend on the severity of the clinical situation and the judgment and experience of the treating physician.

Pregnancies and overdoses should be documented and reported per the SAE reporting guidelines in section 11.4.1 above.

#### 11.5 IND Safety Reports Unrelated to this Trial

IND safety reports not occurring on this trial but involving the study intervention (outside SAEs) received from outside sources will be forwarded to participating sites for submission to their Institutional Review Boards per their guidelines.

## 12. STATISTICAL METHODS

The sections below provide an overview of the statistical considerations and analyses.

### 12.1 Sample Size Determination

For this prospective phase II pilot study, the sample size justification is based on the primary endpoint, the complication rate for evaluable patients who complete surgery. A sample size of 25 patients achieves ~80% to detect a reduction of 20% in the 30-day post-operative complication rate (from 30% to 10%), using a one-sided exact test with a significance level of 0.05. Assuming 10% drop-out rate, we will accrue a total of 28 patients for this study. The study expects a 20-month accrual period with an additional follow-up of 7 months after the last patient is enrolled. The sample size calculation is conducted by PASS 16.

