**STUDY SCHEMA**

NALIRIFOX Cycle Length = 2 weeks  
 Accrual Goal= 28 subjects

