
Accrual Goal:	A total of 28 evaluable subjects.
Inclusion Criteria:	
Individuals eligible for study participation must meet the following criteria:
 
 
A. Written informed consent obtained from the subject and the ability for the subject to comply with all the study-related procedures.
 
B. Both males and females <math>\geq</math> eighteen years of age.
 
C. A new clinical diagnosis of resectable or borderline resectable, previously untreated pancreatic adenocarcinoma confirmed by pathologic specimen evaluation
 
D. No clinical evidence of metastatic disease, confirmed by CT of chest/abdomen and pelvis with IV contrast (or MRI of abdomen and pelvis with non-contrast chest CT, if IV contrast is contraindicated).
 
E. Potentially resectable local disease, confirmed by CT of abdomen with IV contrast (MRI abdomen if CT/contrast is contraindicated). Radiographic confirmation of resectable or borderline resectable pancreatic cancer is verified by documented consensus discussion of the GI Multidisciplinary Tumor Board. The ultimate determination of whether a potential subject meets the criteria of “resectable or borderline resectable” lies in the consensus of the UF GI Multidisciplinary Tumor Board, or equivalent body (for external sites).
 
F. Eastern Cooperative Oncology Group (ECOG) performance status score of 0 or 1.
 
G. Treated biliary obstruction (if applicable).
 
H. Subjects with known or suspected Gilbert’s disease must be formally tested for UGT1A1*28 with results available to study team prior to treatment initiation.
 
I. Adequate organ function; as defined by: 
 
i. Hematologic- 
 
- ANC > 1,500 cells/<math>\mu</math>l without the use of hematopoietic growth factors; and
 
- Platelet count > 100,000 cells/<math>\mu</math>l; and
 
- Hemoglobin > 9 g/dL (blood transfusions are permitted for patients with hemoglobin levels below 9 g/dL)
 
 
 
ii. Hepatic-
 
 
 

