	
this will be compared to expected complication rate. Pre-operative imaging will be compared to the baseline studies to assess radiographic response and continued surgical resectability potential. RECIST Radiographic criteria and clinical evaluations will be used to determine radiographic response and resectability. Surgical resection rates will be calculated and pathologic downstaging will be determined. Biochemical response rates will be calculated by serial CA19-9 levels and characterized as those with normalization of CA19-9 during therapy, reduction without normalization or no reduction with assessment of the temporal nature of these changes and correlation to surgical resection rates. Treatment completion rate will be calculated for all patients and is defined as the completion of all intended treatment cycles. Statistical analyses will be conducted by the study biostatistician using SAS v9.1 (SAS institute, Cary, NC)

Statistical Considerations:	
For this prospective phase II pilot study, the sample size justification is based on the primary endpoint, the complication rate for evaluable patients who complete surgery. A sample size of 25 patients achieves ~80% to detect a reduction of 20% in the 30-day post-operative complication rate (from 30% to 10%), using a one-sided exact test with a significance level of 0.05. Assuming 10% drop-out rate, we will accrue a total of 28 patients for this study. The study expects a 20-month accrual period with an additional follow-up of 7 months after the last patient is enrolled. Subjects failing to proceed to surgery will be replaced, but all will support the secondary analyses. The sample size calculation is conducted by PASS 16.

Estimated Enrollment Period:	20 months
Estimated Study Duration:	27 months

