### 4.1 Number of Subjects

A total of 28 evaluable subjects are to be enrolled.

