### 12.2 Analysis of Primary Endpoint

The primary analysis will use the modified Intention-to-Treat (mITT) population consisting of subjects who are enrolled and received any dose of study medication. The mITT population will be included in summary tables of subject demographics and disease characteristics, and in analysis of efficacy. Subjects who did not progress to surgery (for any reason) or are lost to follow-up will be censored at the day of their last objective tumor assessment and will be unevaluable for the primary endpoint. Subjects failing to proceed to surgery will be replaced, but all will support the secondary endpoints including feasibility, safety and correlative biologic analyses.

Post-operative complications will be measured at the EOT visit 4-6 weeks after surgery. Complications occurring within 30 days after surgery and contributing to the primary endpoint are defined as hospital re-admission, death, second surgery or interventional procedure or major complications extending hospital stay. The proportion and its exact 90% confidence interval of 30-day post-operative complication rate will be calculated. Statistical analyses will be conducted using SAS v9.4 (SAS institute, Cary, NC).

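### The exact test named in Section 12.1 has 76.4% power with 25 evaluable patients, not about 80%, and other sections set the evaluable target at 28

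*Combined protocol and SAP*

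**What the plan says.** Section 12.1 sizes the trial on the 30-day post-operative complication rate among evaluable patients who complete surgery. It states: "A sample size of 25 patients achieves ~80% to detect a reduction of 20% in the 30-day post-operative complication rate". The rates are 30% and 10%, the test is one-sided and exact, and the significance level is 0.05. The word power is missing, but the 80% can hardly mean anything else. The section continues: "Assuming 10% drop-out rate, we will accrue a total of 28 patients for this study". The synopsis, under Statistical Considerations, repeats the calculation.

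Other current text gives a different evaluable number:

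- Synopsis, Accrual Goal: "A total of 28 evaluable subjects".
- Section 4.1: "A total of 28 evaluable subjects are to be enrolled".
- Study Schema: "Accrual Goal= 28 subjects", without saying whether these are evaluable. Section 3.1 likewise plans 28 subjects.

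On losses, the synopsis says: "Subjects failing to proceed to surgery will be replaced, but all will support the secondary analyses". Sections 8.1, 8.3 and 12.2 agree that patients who do not complete surgery are replaced. Section 12.2 adds that subjects who do not reach surgery "or are lost to follow-up will be censored at the day of their last objective tumor assessment and will be unevaluable for the primary endpoint". The replacement list in Section 8.3 does not cover patients lost after surgery.

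For the analysis, Section 12.2 plans the observed proportion with an exact 90% confidence interval. No cut-off for the number of complications is printed.

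**The concern.** Two things do not fit together. First, every input to the power statement is given, and the named test does not return the stated power. An exact binomial test on 25 patients moves in whole complications, so its attained size can sit well below 0.05 and its power below what a smooth approximation suggests.

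Second, a reader cannot tell whether accrual ends at 28 enrolled, with about 25 evaluable, or continues until 28 are evaluable. The drop-out allowance does not settle this. Patients who miss surgery are replaced, so it is unclear which losses the 10% is meant to cover.

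At stake are the power that the trial can claim and, because no cut-off is printed, the number of complications that would count as evidence against 30%.

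**Working it through.** **Inputs.** From Section 12.1 and the synopsis: n = 25, p0 = 0.30, p1 = 0.10, one-sided exact test, alpha = 0.05, drop-out 10%. From the synopsis Accrual Goal and Section 4.1: 28 evaluable. From Section 12.2: exact 90% confidence interval.

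**The plan's accrual figure.** 25 / 0.9 = 27.8, rounded up to 28. This reproduces.

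**The plan's power figure.** Let X be the number of patients with a complication. The cut-off c is the largest value with P(X ≤ c | n, 0.30) ≤ 0.05, and power is P(X ≤ c | n, 0.10).

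At n = 25:

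- P(X ≤ 3 | 25, 0.30) = 0.0332, which is allowed.
- P(X ≤ 4 | 25, 0.30) = 0.0905, which is not. So c = 3.
- Power = P(X ≤ 3 | 25, 0.10) = 0.0718 + 0.1994 + 0.2659 + 0.2265 = 0.7636.

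The stated figure of about 80% does not reproduce. The shortfall is 80 − 76.4 = 3.6 points. With c = 3, power reaches 80% only if the true rate is 9.3%.

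**Calculations that come close to 80%.**

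- Normal approximation, null variance, no continuity correction: Φ[(0.20 − 1.645 × √(0.21/25)) / √(0.09/25)] = Φ[(0.20 − 0.1508) / 0.06] = Φ(0.82) = 79.4%. The corresponding required n is 25.3.
- Randomised exact test: (0.05 − 0.0332) / (0.0905 − 0.0332) = 0.293, and 0.7636 + 0.293 × (0.9020 − 0.7636) = 80.4%.

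The plan names neither. A mid-p version of the exact test gives 76.4% again.

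**Other evaluable numbers, same exact test.**

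| Evaluable n | Cut-off | Size | Power | Size at next cut-off |
|---|---|---|---|---|
| 24 | 3 | 0.042 | 78.6% | 0.111 |
| 25 | 3 | 0.033 | 76.4% | 0.090 |
| 26 | 3 | 0.026 | 74.1% | 0.073 |
| 27 | 3 | 0.020 | 71.8% | 0.059 |
| 28 | 4 | 0.047 | 85.8% | 0.113 |

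The smallest number with at least 80% power is 28. Power is not monotone in n: between 24 and 27 the cut-off stays at 3 and power falls with each added patient.

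**Effect on the planned interval.** The upper limit of the exact 90% interval corresponds to the one-sided 0.05 test.

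| Complications / n | Upper 90% limit | Excludes 30%? |
|---|---|---|
| 3 / 25 | 28.2% | yes |
| 4 / 25 | 33.0% | no |
| 4 / 28 | 29.8% | yes |

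If the true rate is 10%, the probability of exactly 4 complications is 0.9020 − 0.7636 = 13.8% at n = 25 and 0.8579 − 0.6946 = 16.3% at n = 28.

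**The case against.** The strongest reply is that the trial as operated may have more power than it claims. If the Accrual Goal and Section 4.1 bind, and patients who miss surgery are replaced, the test has 85.8% power. That is correct, but Section 12.1 and the synopsis would then misstate both the number and the power.

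A second reply is that the approximation sign covers the gap, and that uncertainty in the 30% benchmark matters more. Section 1.1 gives 27–35% with FOLFIRINOX. Against a true rate of 10%, exact power at 25 patients is 53.7% for a 27% null and 90.2% for a 35% null. The second half is fair, and it puts 3.6 points in proportion. It does not make 76.4% the answer that the named test was said to give.

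Third, the exact interval uses whatever denominator is observed, so 4/25 and 4/28 are different data and each has a clear reading. This also stands: once the final denominator is known, nothing is undecided. What is missing is a denominator fixed in advance.

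Finally, the source of the 80% cannot be established. The documents cite PASS 16 without output, and two unnamed calculations come close. No cause should be asserted.

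**Conclusion.** The concern holds. Under the named test, 25 evaluable patients give 76.4% power at a size of 0.033. No number from 20 to 27 reaches 80%, and 28 gives 85.8% at a size of 0.047. Current text sets both 25 and 28 as the evaluable target, and the 10% drop-out is not tied to any defined loss.

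This rests on taking the 80% as power, on a non-randomised exact binomial test against a fixed 30%, and on a true rate of 10%. Reading Section 12.2 as leaving losses after surgery unreplaced is an inference from the list in Section 8.3; the text says only lost to follow-up.

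Type I error is below 0.05 at either number and the study is a pilot, so this should be corrected but does not threaten the validity of the analysis.

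**What to change.** Choose one evaluable number and state it with its cut-off, size and power in Section 12.1, the synopsis and Section 4.1.

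- **Option 1, following Section 12.1.** Keep 25 evaluable of 28 accrued. Restate power as 76%, with a cut-off of 3 of 25 and a size of 0.033. Change the Accrual Goal and Section 4.1 to 28 accrued, 25 evaluable. This is wording only; the price is a less favourable power figure.
- **Option 2, if 28 evaluable is intended.** State a cut-off of 4 of 28, size 0.047 and power 85.8%. If the full 10% is lost beyond replacement, accrual becomes 28 / 0.9 = 31.1, so 32, or 4 more subjects with drug supply. At the planned 28 / 20 = 1.4 per month that takes 32 / 1.4 = 22.9 months, and 29.9 months with the 7 months of follow-up, against 20 and 27 now. With no such loss the extra is nil, so the range is 0 to 4 subjects. The Study Schema and Sections 3.1 and 12.1 would need the new accrual number.

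Under either option:

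- Say that replacing patients who miss surgery can take enrolment above the stated accrual.
- Define the 10% as losses not covered by replacement, for example loss to follow-up after surgery.
- State that the exact critical value at the final evaluable number applies, since both cut-off and power change with it.

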A major challenge in treating patients with aggressive combination neoadjuvant therapy relates to toxicity, recognizing that patients need to be capable of receiving full doses and cycles of therapy to ensure optimal down staging and micrometastatic sterilization, yet still be capable of safely undergoing a major surgical resection. The most active therapy (inclusive of survival and response rates) in the metastatic setting is demonstrated by use of FOLFIRINOX therapy (5-fluorouracil, leucovorin, oxaliplatin and irinotecan), but it typically requires routine dose modifications, delays and growth factor support. Commonly, the irinotecan component of this polyagent therapy is reduced or dropped in clinical practice when toxicities develop, leading to several “modified” FOLFIRINOX regimens in use. When used in the neoadjuvant setting, FOLFIRINOX regimens consistently require dose modifications (65%), but still demonstrate meaningful clinical down staging and surgically negative margins (70% R0 resection rate). However, toxicity limits the number of pre-operative cycles that can be delivered and post-operative complications are not trivial. Even at high to very high volume centers, 30-day post-operative mortality secondary to pancreatic resection is in the range of 3.8-7.5%. In addition to this, clinically significant complications including delayed gastric emptying (15-17%), bile leak (1-2%), and pancreatic fistula (2-22%) may require either prolonged hospitalization or readmission. With the addition of FOLFIRINOX, even at modified doses, this complication rate is as high as 27-35%. Such post-operative complications limit the ability to provide further adjuvant systemic therapy or radiotherapy.

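### The 30% historical rate used as the null in section 12.1 is not shown to be measured on the trial's own 30-day composite endpoint

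*Combined protocol and SAP*

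**What the plan says.** **The null.** Section 12.1 sizes the trial to "detect a reduction of 20% in the 30-day post-operative complication rate (from 30"%, citing references 16 and 18, "to 10%), using a one-sided exact test with a significance level of 0.05". It states: "A sample size of 25 patients achieves ~80"% power. The synopsis repeats the calculation and says of the observed rate that "this will be compared to expected complication rate".

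**What the protocol says the historical rate is.** Section 1.1 first gives 30-day mortality after pancreatic resection (3.8-7.5%). As an addition to that, it lists clinically significant complications: delayed gastric emptying (15-17%), bile leak (1-2%), "and pancreatic fistula (2-22%) may require either prolonged hospitalization or readmission". It then says: "With the addition of FOLFIRINOX, even at modified doses, this complication rate is as high as 27-35"%, citing references 15-18, a range that includes the two sources of the 30%. It gives no time window, no severity grade, and no statement on whether deaths or re-interventions are counted.

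**The endpoint.** Section 12.2 counts events within 30 days of surgery, "defined as hospital re-admission, death, second surgery or interventional procedure or major complications extending hospital stay". Section 2.1 gives the same components. The planned summary is the proportion with an exact 90% confidence interval.

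**The concern.** The benchmark, as section 1.1 describes it, and the endpoint differ in three respects:

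- The benchmark covers complications for which a longer stay or readmission is only a possible consequence. A complication counts in the endpoint only if it leads to one of the listed outcomes.
- The endpoint includes death. Section 1.1 reports death apart from the complication rate.
- The endpoint has a 30-day window. Section 1.1 states none for the 27-35%.

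Nothing in the protocol says that the 30% was counted, or recounted, on the endpoint's components. If the composite's historical rate is not 30%, the success threshold is misplaced. With a lower true rate, a regimen that changes nothing can beat 30% more often than the nominal 5%. With a higher true rate, the test is stricter than intended.

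**Working it through.** **Inputs.** From section 12.1: null p0 = 0.30, target p1 = 0.10, one-sided exact test at 0.05, n = 25 evaluable. From section 1.1: mortality 3.8-7.5%. Assumed, because the documents do not give it: the composite's historical rate, varied from 20% to 37.5%.

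**Step 1: the plan's rule.** Let X be the number of patients with an event, X ~ Bin(25, p). The cutoff c is the largest value with P(X ≤ c | p0) ≤ 0.05.

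- P(X ≤ 3 | 0.30) = 0.0001 + 0.0014 + 0.0074 + 0.0243 = 0.033.
- P(X ≤ 4 | 0.30) = 0.033 + 0.057 = 0.090, above 0.05.

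So success means at most 3 events in 25, with exact level 3.3%. Power is P(X ≤ 3 | 0.10) = 0.0718 + 0.1994 + 0.2659 + 0.2265 = 0.764. The stated ~80% is not reproduced by the exact test; the uncorrected one-sided normal approximation gives 79.4%. That shortfall is a separate matter and is not used below.

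**Step 2: the confidence interval.** At 3/25 the exact (Clopper-Pearson) 90% limits are the Beta(3, 23) 5th percentile, 3.4%, and the Beta(4, 22) 95th percentile, 28.2%. The interval excludes 30% but not 25%. At 4/25 the upper limit is 33.0%. The interval planned in section 12.2 therefore gives the same decision as the one-sided 5% test in section 12.1.

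**Step 3: keep the rule, vary the composite's historical rate.** With no true benefit, the chance of success is P(X ≤ 3 | n = 25, p). The last two columns reset the null to p, find the new exact cutoff at n = 25, and recompute power at 10%.

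| Composite's historical rate p | Chance of success, no benefit, rule ≤ 3/25 | Exact cutoff if null = p | Power at 10% with that cutoff |
|---|---|---|---|
| 20% | 23.4% | ≤ 1 | 27% |
| 25% | 9.6% | ≤ 2 | 54% |
| 27% | 6.4% | ≤ 2 | 54% |
| 30% (plan) | 3.3% | ≤ 3 | 76% |
| 33.8% (30% + 3.8%) | 1.3% | ≤ 4 | 90% |
| 37.5% (30% + 7.5%) | 0.5% | ≤ 4 | 90% |

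The last two rows add the section 1.1 mortality range to 30% and assume that no patient is counted in both.

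**Step 4: 28 evaluable patients.** Section 4.1 speaks of 28 evaluable subjects. The cutoff is then ≤ 4 (P(X ≤ 4 | 28, 0.30) = 4.7%; ≤ 5 gives 11.3%). With no benefit, P(X ≤ 4 | 28, p) is 9.1% at 27%, 13.5% at 25% and 31.5% at 20%. The pattern is the same.

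**The case against.** The best defence is that section 1.1 is background prose and its back-reference is loose. It can be read as meaning complications that do prolong stay or cause readmission, which are components of the composite. Section 12.1, which actually sets the null, calls the 30% a 30-day post-operative complication rate, and section 12.2 uses the same label for the endpoint. The trial is also a pilot, and section 12.2 plans only a proportion and an interval.

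Part of this stands. The definitions in references 16 and 18 are not in the documents, so a mismatch cannot be asserted as fact. But a shared label is not a shared definition, and no section supplies one. The pilot status does not remove the comparison either: the synopsis plans it, section 12.1 sizes for it, and the interval carries it out.

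A reader might infer four stronger things that the documents do not support:

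- **That the trial could succeed only because its endpoint is narrower.** Leaving out complications without a listed consequence lowers the composite's rate, but adding deaths and re-interventions raises it. The net direction is unknown.
- **That a 10% target below the 15-17% delayed-gastric-emptying rate proves that null and target are on different scales.** Section 1.1 names delayed gastric emptying among events that may prolong stay, so such cases can count in the composite. The 15-17% is a background figure for pancreatic resection; 10% is a hypothesised target. An ambitious target is not evidence of mixed scales.
- **That mortality should be added to the 10% target, with a large loss of power.** The 10% is set for an endpoint that already includes death, so this would count deaths twice.
- **That the comparison with 30% should move to a separate rate of clinically significant complications.** The protocol does not define that rate. Section 11.2 limits adverse-event reporting beyond 30 days after the last dose to unexpected, procedure-related events, while surgery falls 4-8 weeks after the last dose. The data may not be collected.

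**Conclusion.** The point holds as a gap in the justification of the null: the protocol does not show that 30% is the historical rate of the trial's own endpoint, and its only description of that rate differs from the endpoint in components, in the handling of death and in the time window. It does not establish that two different outcomes are being compared, or which way any error runs.

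The consequence can be material. Under the 3-of-25 rule, a historical composite rate only three points below 30% already takes the chance of success without benefit above 5% (6.4%); at 20% it is 23.4%. If deaths instead raise the rate to 33.8%, it is 1.3%. These figures rest on the exact binomial rule implied by section 12.1 and on an assumed range for the composite's rate.

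**What to change.** In section 12.1 and the synopsis, re-derive the null from references 16 and 18 by counting the trial's own composite within 30 days of surgery. State the definition and window used, then restate the exact cutoff and exact power for that null.

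If those series do not report the components, say so and keep the composite as the primary endpoint. In section 12.2, report it with its exact 90% interval and tabulate the success probability over a stated range of nulls, for example 20-35%. A result below 30% should then not be attributed to a treatment-related reduction without a caveat that the benchmark's definition could not be matched.

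The cost is re-reading two papers, a few sentences and one table; no more patients and no new data collection. The downside is that the benchmark or the stated power may become less favourable: at n = 25, power against 10% would be 54% with a 25% null and 27% with a 20% null.
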